Visit Number/Description	Year 2, Week 1, Day 1	Year 2, Week 1, Day 2	Year 2, Week 1, Day 4	Year 2, Week 1, Day 6	Year 2, Week 1, Day 7	Year 2, Days 8 & 9	Year 2, Day 10	Year 2, Day 14	Year 2, Week 3	Year 2, Week 4	Year 2, Week 5	Year 2, Week 6	Year 2, Week 7	Year 2, Week 9	Year 2, Week 11	Year 2, Week 13	Year 2, Week 18	Year 2, Week 35	Year 2, Week 52	Years 3, 4, 5, 6 ^d	Years 3, 4, 5, 6 ^d				
Visit Day	390	391	393	395	396	397& 398	399	403	410	417	423	431	437	449	463	479	509	629	749	930, 1290, 1650, 2010 ^d	1110, 1470, 1830, 2190 ^d				
Visit Window (\pm days)	3 ^f	2 ^f	2 ^f	2 ^f	2 ^f	2 ^f	2 ^f	2 ^f	3 ^f	3 ^f	3 ^f	3 ^f	3 ^f	3 ^f	3 ^f	3 ^f	3 ^f	3 ^f	7 ^f	7 ^f	7 ^f	30 ^f	30 ^f		
Study Interventions																									
Protocol-mandated glucocorticoid regimen ^q	X	X	→	→	→	→	→	→	→	→	→	→	→	→	→	→	→	→	→	X					
Background glucocorticoid regimen																				X	→	→	→	X ^v	X ^v
IP administration	X																								
Ongoing monitoring																									
Concomitant medications	→	→	→	→	→	→	→	→	→	→	→	→	→	→	→	→	→	→	→	→	→	→	→	X	
Serious and nonserious adverse event monitoring	→	→	→	→	→	→	→	→	→	→	→	→	→	→	→	→	→	→	→	→	→	→	→	X	

Abbreviations/Acronyms: →=continuous monitoring/event; AAV9= adeno associated virus serotype 9; ADA=anti-drug antibody; BP=Blood pressure; CG=Caregiver; CGIS=Clinician Global Impression of Severity; CBCL=Child Behavior Check List; ECG = electrocardiogram; ELISpot= Enzyme-Linked ImmunoSpot; EQ-5D-Y= EuroQol 5 Dimensions–Youth; FVC= Forced Vital Capacity; IP=investigational product; NAb=neutralizing antibodies; NSAA=North Star Ambulatory Assessment; PGIS= patient global impression of severity; PODCI=Pediatric Outcomes Data Collection Instrument; PR=pulse rate; temp=temperature.

a. Visit 20 – Year 2, Week 1, Day 1

- Prior to IP administration, the Investigator must confirm applicable Year 2 IP administration eligibility criteria (Section 7.1);
- Participants are to be admitted to the site;
- Participants will be instructed not to take their background glucocorticoid dose on Day 390 (Visit 20);
- The following assessments must be performed **prior to IP administration**: Physical examination, blood collection (ELISpot to mini-dystrophin and AAV9), urine sample collection, ECG and vital signs;

Period	Year 2																				Long-term follow up	Early Discontinuation Visit

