 - a. Absolute neutrophil count <1000 cells/mm³;
 - b. Platelets <150 x 10³/μl;
 - c. Cystatin C >1.2 x ULN;
 - d. Positive hepatitis A virus (anti-HAV) immunoglobulin M, hepatitis B surface antigen (HbsAg), and/or hepatitis C antibody (HCVAb);

e. Markers of hepatic inflammation or overt or occult cirrhosis as evidenced by one or more of the following:

1. Prothrombin time (PT) > upper limit of normal (ULN); prolonged international normalized ratio (INR) >ULN;
2. GLDH >2 x ULN;
3. Total bilirubin >1.5 x ULN (unless the participant has a history of Gilbert disease) and direct bilirubin >0.5 mg/dL;
4. Gamma-glutamyl transferase (GGT) >1.5 x ULN.

9. Other acute or chronic medical or psychiatric condition at Screening (Visit 1), including recent (within the past year) or active suicidal ideation or behavior (using screening by the Child Behavior Check List (CBCL) and determined by the Investigator, as described in [Section 8.2.13](#)) or laboratory abnormality that may increase the risk associated with study participation or IP administration or may interfere with the interpretation of study results and, in the judgment of the Investigator, would make the participant inappropriate for entry into this study.

10. Acute infection at Screening (Visit 1) or Baseline (Visit 2) that, in the judgement of the Investigator is not expected to be fully resolved at least 2 weeks before Day 1 (Visit 3). At Day 1 (Visit 3), participants must have been infection-free for at least 2 weeks prior to IP administration. Delay of IP administration for up to 14 days is permitted to enable infections to become fully resolved.

11. Investigator site staff members directly involved in the conduct of the study and their family members, site staff members otherwise supervised by the Investigator, or Pfizer employees, including their family members, directly involved in the conduct of the study.

12. Known hypersensitivity to any of the components of the IP or solution for infusion, such as hypersensitivity to albumin or a diagnosis of HFI. Symptoms suggestive of HFI include nausea, vomiting, bloating, stomach cramps, or diarrhea following the ingestion of sweet foods or drinks, or a pattern of avoiding sweet foods or drinks.

13. Contraindication to the use of eculizumab, as per the local prescribing information.

14. LVEF <50% on echocardiogram performed at the Screening Visit (Visit 1), as evaluated by the central reader.

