6.1.1. Administration

PLEASE NOTE: Participants will not receive IP if they meet any of the following; (for Year 2 IP administration eligibility, please see [Section 7.1](#)).

1. Receipt of a treatment with gene therapy, defined as any therapy introducing exogenous DNA or intended to permanently alter the endogenous DNA between the Screening Visit (Visit 1) and the Day 1 Visit (Visit 3). Participants who receive a treatment with gene therapy between Screening (Visit 1) and Day 1 (Visit 3) will not be eligible for IP administration and will be withdrawn from the study.
2. Receipt of a treatment designed to increase dystrophin expression (including, but not limited to exon-skipping and nonsense read-through) between the Screening Visit (Visit 1) and the Day 1 Visit (Visit 3). Participants who receive a treatment designed to increase dystrophin expression between Screening (Visit 1) and Day 1 (Visit 3) will not be eligible for IP administration and will be withdrawn from the study.
3. Receipt of an investigational drug or investigational vaccine between the Screening Visit (Visit 1) and the Day 1 Visit (Visit 3). Participants who receive an investigational drug or investigational vaccine between Screening (Visit 1) and Day 1 (Visit 3) will not be eligible for IP administration and will be withdrawn from the study.
4. Positive test for NAb to AAV9, based on the threshold determined by the Central Laboratory, at Baseline (Visit 2); if the analysis of NAb to AAV9 was required due to the first blood draw for NAb to AAV9 testing at the Day 1 (Visit 3), or most recent test, if repeat blood draw(s) was required, being more than 55 days after the Screening Visit (Visit 1), please see [Section 1.3.1](#). Participants who have a positive test for NAb to AAV9 will be withdrawn from the study.
5. Receipt of a live attenuated vaccination within 90 days prior to Day 1 (Visit 3). If a participant has received a live attenuated vaccination within 90 days prior to Day 1 (Visit 3), IP administration must be delayed until at least 90 days after the last administration of the vaccine.
6. Receipt of an inactivated vaccine (eg, influenza, meningococcus, pneumococcus, Haemophilus influenzae vaccination) within 30 days prior to Day 1 (Visit 3). If a participant has received an inactivated vaccine within 30 days prior to Day 1 (Visit

3), IP administration must be delayed until at least 30 days after the last administration of the vaccine.

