7. Receipt of an mRNA or DNA-based, or non-replicating viral vector vaccine (eg, against SARS-CoV2) within 30 days prior to Day 1 (Visit 3). If a participant has received any of the above-listed vaccines within 30 days prior to Day 1 (Visit 3), IP administration must be delayed until at least 30 days after the last administration of the vaccine.
8. Receipt of any systemic immunosuppressant agents other than glucocorticoids, and/or, systemic antiviral, and/or interferon therapy. If a participant has received any of the above-listed therapies within 30 days prior to Day 1 (Visit 3), IP administration must be delayed until at least 30 days after the last dose.
9. Acute infection at Day 1 (Visit 3). At Day 1 (Visit 3), participants must have been infection-free for at least 2 weeks. Delay of IP administration for up to 14 days is permitted to enable infections to become fully resolved.
10. Participants with a myocarditis diagnosed by a pediatric cardiologist between Screening (Visit 1) and Day 1 (Visit 3) will not be eligible for IP administration and will be withdrawn from the study.

Per the treatment assignment dosing schedule, participants will be admitted to the site to receive a single intravenous infusion of IP delivered over approximately 2 to 4 hours (-15 minutes or +30 minutes including flush), at a rate no more than 125 mL/hour, at Day 1 (Visit 3) and Day 390 (Visit 20), in accordance with the [Schedule of Activities](#), and will be monitored as described in [Section 8.2.10](#).

In lieu of their background glucocorticoid regimen, participants will receive an intravenous infusion of 2 mg/kg of methylprednisolone, 1 to 4 hours prior to infusion of IP, followed by the protocol mandated glucocorticoid regimen for 3 months, as described in [Section 6.5.1](#).

IP shipment will be initiated once the body weight is entered into the interactive response technology drug management system. The appropriate amount of IP, based on the actual concentration for the lot and participant's body weight (at Baseline (Visit 2) for Year 1 IP administration and at Day 328 (Visit 18) for Year 2 IP administration), will be prepared and administered in a solution of approximately 250 to 500 mL containing 1.25% human serum albumin. Appropriate medication and other supportive measures for management of an unexpected reaction to the infusion should be available in accordance with local guidelines.

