Cohort 1 participants, as confirmed by the unblinded medical monitor, will not receive Year 2 IP administration, placebo, if they meet exclusion criterion 15. They will not require post-IP safety monitoring in Year 2, will not attend Visit 18 in Year 1 and Visits 20 to 30.2 in Year 2, and will not receive their protocol-mandated glucocorticoid regimen in Year 2. These participants will remain in the study for safety monitoring as described in [Appendix 12](#).

Once the unblinded medical monitor has communicated to the Investigator that the participant meets eligibility criteria based on laboratory tests and echocardiographic results, then the Investigator will ensure that none of the criteria listed below are met before allowing IP administration.

To preserve the blinding of the treatment assignment for the site and for the Sponsor, the following criteria will be assessed for both Cohort 1 and Cohort 2 participants.

7. Receipt of a live attenuated vaccination within 90 days prior to Day 390 (Visit 20). If a participant has received a live attenuated vaccination within 90 days prior to Day 390 (Visit 20), IP administration must be delayed until at least 90 days after the last administration of the vaccine.
8. Receipt of an inactivated vaccine (eg, influenza, meningococcal, pneumococcal, *Haemophilus influenzae* vaccination) within 30 days prior to Day 390 (Visit 20). If a participant has received an inactivated vaccine within 30 days prior to Day 390 (Visit 20), IP administration must be delayed until at least 30 days after the last administration of the vaccine.
9. Receipt of an mRNA or DNA-based, or non-replicating viral vector vaccine (eg, against SARS-CoV2) within 30 days of Day 390 (Visit 20). If a participant has received any of the above-listed vaccines within 30 days prior to Day 390 (Visit 20), IP administration must be delayed until at least 30 days after the last administration of the vaccine.
10. Receipt of any systemic immunosuppressant agents other than glucocorticoids, and/or systemic antiviral therapy, and/or interferon. If a participant has received any of these therapies, IP administration must be delayed until at least 30 days after the last dose.
11. Acute infection at Day 360 (Visit 19) that, in the judgement of the Investigator, is not expected to be fully resolved at least 14 days prior to IP administration on Day 390 (Visit 20).

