12. Additionally, any participant, in Cohort 1 or Cohort 2, who has received gene therapy (other than IP) after Year 1 IP administration will not be eligible for Year 2 IP administration but will not be withdrawn from the study.

If any of the above eligibility criteria (7-11) are met for Cohort 1 or Cohort 2 participants, IP administration will be delayed until none of the criteria are met. If the time between the blood draw for the clinical safety laboratory tests on Day 360 Visit (Visit 19) and the planned Day 390 Visit (Visit 20) exceeds 13 weeks (90 days), due to operational or administrative reasons (eg, enrollment pause due to regulatory or safety review, operational issues causing significant delays), then the clinical safety laboratory tests should be repeated and eligibility (re)confirmed prior to administering IP. The participant will not be withdrawn due to exceeding the time between Day 360 Visit (Visit 19) and Day 390 Visit (Visit 20).

If a Cohort 2 participant is determined to be *permanently* ineligible for Year 2 IP administration, because of a confirmed result for the hematology or chemistry profiles outside allowable limits or because of a positive test for NAb to AAV9, based on the threshold determined by the Central Laboratory, he will be withdrawn from the study. The medical monitor will inform the site of the decision, to allow the site to communicate with the participant and the caregiver. In this circumstance, no Early Discontinuation Visit will be required.

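### The Year 2 infection criterion looks only at infections present at Visit 19, so an infection starting later need not delay dosing, unlike in Year 1

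*Protocol*

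**What the plan says.** Section 7.1 lists the Year 2 criteria that the investigator checks for both cohorts. It introduces them by saying that "the Investigator will ensure that none of the criteria listed below are met before allowing IP administration". If any of criteria 7 to 11 is met, "IP administration will be delayed until none of the criteria are met".

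Criterion 11 is the infection criterion: "Acute infection at Day 360 (Visit 19) that, in the judgement of the Investigator, is not expected to be fully resolved" at least 14 days before the Day 390 dose. Criterion 10 postpones dosing until 30 days after the last dose of a systemic antiviral, interferon or non-glucocorticoid immunosuppressant.

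The Year 1 rule is worded differently. Section 5.2, exclusion 10, has a similar forecast for infections at Screening or Baseline, and then adds that at Day 1 "participants must have been infection-free for at least 2 weeks prior to IP administration". Section 6.1.1, item 9, repeats this as a check on the dosing day: "At Day 1 (Visit 3), participants must have been infection-free for at least 2 weeks". Section 6.1.1 does not carry over to the second infusion; its opening note says "for Year 2 IP administration eligibility, please see" Section 7.1.

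**The concern.** Year 2 keeps the forecast half of the Year 1 infection rule and drops the dosing-day half. The document gives no reason for a weaker rule at the second infusion. The exposure there is not smaller: Cohort 2 (about 33 boys, if still eligible) receives the active vector, and under Section 6.5.1 both cohorts receive 2 mg/kg intravenous methylprednisolone followed by 2 mg/kg/day oral prednisone or prednisolone through Day 15. A site that follows Section 7.1 to the letter could therefore give vector and high-dose glucocorticoid within 14 days of an infection that would have barred dosing in Year 1, without a protocol deviation.

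**Working it through.** The plan states no figure to reproduce. The check is a comparison of wording plus visit arithmetic.

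**Inputs.** Visit 19 is Day 360 ± 7 (Section 1.3.1). Visit 20 is Day 390 ± 3 (Section 1.3.2). The infection-free interval is 14 days (7.1, criterion 11) or 2 weeks (5.2, exclusion 10; 6.1.1, item 9). After a pause, a repeat eligibility visit is required if Visit 19 was more than 90 days earlier, and Visit 20 should follow that visit within 30 days (5.3.2).

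**Step 1: gap from Visit 19 to the Year 2 dose.**
- Nominal: 390 − 360 = 30 days
- Shortest in window: (390 − 3) − (360 + 7) = 387 − 367 = 20 days
- Longest in window: (390 + 3) − (360 − 7) = 393 − 353 = 40 days

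**Step 2: where the 14-day interval falls.** Nominally it starts at 390 − 14 = Day 376. In the tightest schedule it starts at 387 − 14 = Day 373, against Visit 19 on Day 367. So in every in-window schedule the whole 14-day interval lies after the visit to which the criterion is tied.

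**Step 3: reference points within the Section 7.1 list.**

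| Criterion | Subject | Counted relative to |
|---|---|---|
| 7 | Live attenuated vaccine | 90 days back from Visit 20 |
| 8, 9 | Inactivated; mRNA, DNA or viral-vector vaccine | 30 days back from Visit 20 |
| 10 | Immunosuppressant, antiviral, interferon | 30 days from last dose to infusion |
| 11 | Acute infection | Present at Visit 19 |

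Only criterion 11 is tied to Visit 19.

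**Step 4: apply the list.** Take an infection that starts after Visit 19 and resolves x days before the dose, with x below 14. Criteria 7 to 9 concern vaccines and do not apply. Criterion 10 applies only if one of its named therapies was given. Criterion 11 does not apply, because the infection was not present at Visit 19. The delay rule is then not triggered. The Section 6.1.1, item 9, standard applied at the same dose would postpone it until x reaches 14. The same holds for an infection that was present at Visit 19 and expected to clear in time but did not, unless the investigator chooses to revisit the forecast.

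**Step 5: other Year 2 text.** Section 1.3.2, footnote a, requires the investigator to confirm the Section 7.1 criteria before the Visit 20 infusion. Section 5.3.2 does the same after a pause. Neither adds an infection check.

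**Step 6: pauses.** Visit 19 can be up to 90 days old before a repeat eligibility visit is required. Criterion 4 (ejection fraction) is expressly extended to that unplanned visit; criterion 11 is not. Even if criterion 11 is read as applying again there, up to 30 days remain before Visit 20.

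**The case against.** The strongest case is that the practical exposure is small. The boy is admitted and has a physical examination and vital signs, including temperature, before the infusion. Adverse events and concomitant medications are recorded continuously. Section 8 asks for immediate safety concerns to be discussed with the sponsor, and after a pause Section 5.3.2 asks the investigator to confirm that the product can be given. An overt infection would very likely be seen and dosing postponed. This stands, and it narrows the gap mainly to the infection that has recently resolved. None of these safeguards requires 14 infection-free days.

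Criterion 10 also does real work. A later infection treated with a systemic antiviral or interferon forces a 30-day wait, longer than the Year 1 interval. It does not reach an infection managed without one of the listed therapies.

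Once the last neutralizing antibody sample is more than 55 days old, a new negative test is mandatory (7.1, criterion 1). That brings another participant contact before a delayed dose, but it is not an infection check.

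A reader might infer that Year 2 has no 14-day margin at all, or that every infection after Visit 19 escapes the rules. The text supports neither: criterion 11 sets a 14-day margin, by forecast, for infections present at Visit 19, and criterion 10 catches some later ones.

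**Conclusion.** The point holds as a wrongly anchored eligibility rule. For an infection that starts after Visit 19, or one whose resolution was misjudged, and that was not treated with a criterion 10 therapy, none of the 14 infection-free days required in Year 1 is required in Year 2. The uncovered interval is 30 days nominally, 20 to 40 in window, and longer after a pause.

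It should be fixed, but it is a participant-safety point only. A reader might look for an effect on the trial's conclusions; there is none, because the Year 2 infusion comes after the Week 52 assessment, so the primary endpoint, alpha and power do not change. A reader might also want a count of affected boys. The document gives no infection rate or duration and does not quantify the added risk from a recently resolved infection, so no count is offered. The case rests on the mismatch with the sponsor's own Year 1 rule.

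The conclusion covers the main body of the protocol. Most of the country appendices, and Appendix 12, were not available for this check.

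**What to change.** Keep the Visit 19 forecast in criterion 11 and add a sentence matching Section 6.1.1, item 9: *At the actual Year 2 IP administration (Visit 20, including after a pause), participants must have been infection-free for at least 14 days; otherwise IP administration is delayed until this is met.* The existing delay rule for criteria 7 to 11 then applies as it stands.

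The cost is some later Year 2 doses, at times with product already shipped on the Visit 18 weight. For an infection resolved by the planned Visit 20 the delay is at most 14 days. Let k be the number of days an infection lasts beyond the planned Visit 20. The age of the Visit 19 neutralizing antibody sample at dosing is then at most gap + 14 + k, against the 55-day limit:

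- Gap 20: 34 + k, repeat test if k > 21
- Gap 30: 44 + k, repeat test if k > 11
- Gap 40: 54 + k, repeat test if k > 1

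So an infection resolved by the planned visit (k = 0) stays within the limit even at the longest in-window gap (54 days), and a repeat test is needed only occasionally.

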7.1.1. Temporary Discontinuation

Not applicable.

7.1.2. Rechallenge

Not applicable.

7.2. Participant Discontinuation/Withdrawal From the Study

A participant may withdraw from the study at any time at his own request.

Reasons for discontinuation from the study include the following:

- Refused further follow-up;
- Lost to follow-up;
- Death;
- Study terminated by Sponsor;
- Participant is determined to be not eligible for Year 1 (Cohort 1 and Cohort 2 participants) or Year 2 IP administration (only for Cohort 2 participants).

- Participants randomized before the approval of protocol amendment 6, but not dosed, will be withdrawn from the study if they meet exclusion criterion 15, based on the retrospective review of the results of the genetic testing by the investigator.

If a request is made to withdraw from the study, an alternative to withdrawal should be offered that would enable the collection of key data, including adverse events. Alternative methods may include phone contact with the participant and/or caregiver. Documentation should be made that all alternatives have been offered to the participant and/or caregiver.

At the time of discontinuing from the study, if possible, an early discontinuation visit should be conducted. See the [SoA](#) for assessments to be collected at the time of study discontinuation and follow-up and for any further evaluations that need to be completed.

The Early Discontinuation Visit applies only to participants who are enrolled/randomized and then are prematurely withdrawn from the study, except participants withdrawn because they do not fulfil eligibility criteria for Year 1 ([Section 6.1.1](#)) or Year 2 administration (only Cohort 2 participants) ([Section 7.1](#)). Participants should be queried regarding their reason for withdrawal. The participant will be permanently discontinued both from the study intervention and from the study at that time. Lack of completion of all or any of the withdrawal/early termination procedures will not be viewed as protocol deviations so long as the participant's safety was preserved.

If a participant withdraws from the study, he may request destruction of any remaining samples, taken and not tested, and the Investigator must document any such requests in the site study records and notify the Sponsor accordingly.

If the participant withdraws from the study and also withdraws consent (see [Section 7.2.1](#)) for disclosure of future information, no further evaluations should be performed and no additional data should be collected. The Sponsor may retain and continue to use any data collected before such withdrawal of consent.

Lack of completion of all or any of the withdrawal/early termination procedures will not be viewed as protocol deviations so long as the participant's safety was preserved.

